8. SAFETY ENDPOINTS

Safety analysis will be conducted on safety population and by study lens worn when appropriate.

8.1. Adverse Events

Listings of all reported ocular and non-ocular AEs will be created. There will be separate listings for serious and significant ocular adverse events.

8.2. Slit-Lamp Findings

Any result of the slit-lamp assessment recorded at the entrance and the exit of each visit including unscheduled visits will be tabulated at eye level. Possible findings will be reported in the following order:

- Corneal Infiltrates
- Corneal Edema
- Corneal Neovascularization
- Corneal Neovascularization Location
- Corneal Staining
- Corneal Staining Location
- Conjunctival Injection
- Tarsal Abnormalities
- Other Complications

Findings tabulated as Other Complications will be specified in the listing.

8.3. Entrance and Exit Visual Acuity (LogMAR)

Recorded visual acuity at the entrance and exit of each visit including unscheduled visits will be tabulated at eye level and subject level.

8.4. Unscheduled Lens Replacement and Lens Damage

The number of unscheduled lens replacements, folded lenses and damaged lenses will be tabulated separately by lens at eye level and subject level. For damaged lenses, the damage type and its location will be reported.

8.5. Product Quality Complaints

All reported product quality complaints will be tabulated by lens and lot number at subject level.

9. OTHER ENDPOINTS

9.1. Lens Fitting Characteristics

Mechanical lens fitting characteristics including lens centration, lens movement and overall lens fitting acceptability at fitting evaluation (Visit 1) will be summarized on the safety population by study lens using frequency tables.

9.2. Contact Lens Corrected Visual Acuity (LogMAR)

Monocular and binocular contact lens corrected distance visual acuity measured at Visit 1 will be summarized on the safety population by study lens using descriptive statistics.

9.3. Vision and Nighttime Driving Questionnaire

Individual items of vision and nighttime driving questionnaire will be summarized on the PP population by study lens using frequency tables of rating categories.

9.4. Pupil Diameter

All pupil diameter measures from visit 2, 3 and 3 will be summarized at the eye level by study lens and luminance level (high and low luminance).

9.5. Lighting Levels

10. MEASURES OF AMBIENT LIGHT LEVELS AT THE DRIVING TRACK WILL BE SUMMARIZED DESCRIPTIVELY BY STUDY LENS, DRIVING TIME AND LOCATION (I.E. INSIDE AND OUTSIDE THE VEHICLE) REPORTING CONVENTIONS

P-values greater or equal than 0.0001 will be reported to 4 decimal places; p-values less than 0.0001 will be reported as "<0.0001". All percentages will be reported to one decimal place. The mean and median will be reported to one decimal place greater than the original data. The standard deviation will be reported to two decimal places greater than the original data. Minimum and maximum will use the same number of decimal places as the original data.

11. QUALITY ASSURANCE MEASURES

11.1. Statistical Programming

The statistical programming will follow analysis dataset specification as well as table shell specification. To ensure the validity of the analysis datasets as well as table and listing results, an independent program reviewer will be designated.

11.2. Statistical Analysis

All statistical analyses will be reviewed by a second statistician to ensure proper execution and compliance to the analysis planned in the SAP. The executive summary will be reviewed by a second statistician to ensure the interpretations of the statistical analysis results are valid.

11.3. Changes in the Planned Analysis

The analysis will be conducted according to that specified in above sections. If for any reason a change is made, the change will be documented in the study report along with a justification for the change.

APPENDIX A SAS SYNTAX CODE

Primary Endpoint:

Overall driving performance scores

PROC GLIMMIX DATA = ads plots=studentpanel; CLASS driveseq asper trta carry1a parcat5 subjid sexn; MODEL aval= age sexn driveseq|parcat5 asper|parcat5 trta|parcat5 carry1a|parcat5/ DDFM=KR2 S; RANDOM INTERCEPT / SUBJECT=subjid; **RANDOM INTERCEPT / SUBJECT = parcat5(subjid);** *only included if ANTE(1) is used; RANDOM asper / RESIDUAL SUBJECT=parcat5(subjid) TYPE=covariance matrix group=parcat5; **Remove GROUP = time from the statement above if the test for homogeneity is rejected at 5% significance level; COVTEST "Common Varaince" Homogeneity; **test for homogeneity used along with GROUP = time; LSMEANS trta*parcat5 /slicediff = parcat5 CL ; **Primary analysis; ESTIMATE "Night: Test vs Control1" trta -1 0 1 trta*parcat5 0 -1 0 0 0 1 / CL; **Other Analysis; ESTIMATE "Day: Test vs Controll" trta -1 0 1 trta*parcat5 -1 0 0 0 1 0, "Day: Test vs Control2" trta 0 -1 1 trta*parcat5 0 0 -1 0 1 0, "Night: Test vs Control2" trta 0 -1 1 trta*parcat5 0 0 0 -1 0 1 / ADJUST= bonferroni CL;

RUN;

Where ads: Analysis data set subjid: subject identification aval: overall driving performance score sexn: Gender driveseq: Lens wear sequence (6 levels) asper: Study Period (3 levels) trta: Study lens type (Test, Control1, Control2) parcat5: Driving time (day or night) carry1a: First order carryover effect covariance_matrix: CS, CSH, UN and ANTE(1). The covariance structure that returns the lowest AICC will be selected as the structure that best fit the data.

Secondary Endpoints:

Binocular distance visual acuity (LogMAR)

PROC GLIMMIX DATA = ads plots=studentpanel; CLASS TSEQPG2 aperiod trta carry1a subjid sexn ; MODEL aval= age sexn tseqpg2 aperiod trta carry1a / DDFM=KR2 ; RANDOM INTERCEPT / SUBJECT=subjid; *only included if ANTE(1) is used; RANDOM aperiod / RESIDUAL SUBJECT=subjid TYPE=covariance_matrix ; LSMEANS trta / CL; ESTIMATE "Test vs Control1" trta -1 0 1, *secondary analysis; "Test vs Control2" trta 0 -1 1 / CL; *other analysis; RUN; Where ads: Analysis dataset subjid: subject identification sexn: Gender tseqpg2: Lens wear sequence (6 levels) aperiod: Study Period (3 levels) trta: Study lens type (Test, Control1, Control2) carry1a: First order carryover effect covariance_matrix: CS, CSH, UN and ANTE(1). The covariance structure that returns the lowest AICC will be selected as the structure that best fit the data.

Low Luminance contrast threshold

PROC GLIMMIX DATA= ads;

CLASS tseqpg2 aperiod trta carry1a subjid parcat6 sexn ; MODEL aval/n= age sexn tseqpg2 aperiod trta|parcat6 carry1a / S DIST=BINOMIAL LINK=LOGIT; RANDOM INTERCEPT / SUBJECT=subjid; RANDOM parcat6 / RESIDUAL SUBJECT=aperiod(subjid) TYPE= covariance_matrix; ESTIMATE "Test vs Control1" lens -1 0 1, *secondary analysis; "Test vs Control2" lens 0 -1 1 / CL ILINK EXP; *other analysis;

RUN;

Where ads: Analysis data set n: number of targets subjid: subject identification sexn: Gender tseqpg2: Lens wear sequence (6 levels) aperiod: Study Period (3 levels) trta: Study lens type (Test, Control1, Control2) parcat6: Contrast level (4 levels) carry1a: First order carryover effect covariance_matrix: Compound Symmetry (CS) and Unstructured (UN)

Sign Recognition and Hazard Avoidance

PROC GLIMMIX DATA= ads;

CLASS driveseq asper trta carry1a parcat5 sexn; MODEL aval= age sexn driveseq asper|parcat5 trta|parcat5 carry1a / DDFM=KR2 S DIST=BETA LINK=LOGIT; RANDOM INTERCEPT / SUBJECT=subjid; RANDOM asper / RESIDUAL SUBJECT= parcat5 (subjid) TYPE=covariance_matrix; **Secondary analysis; ESTIMATE "Night: Test vs Control1" trta -1 0 1 trta*parcat5 0 -1 0 0 0 1 / CL ILINK EXP; **Other Analysis; ESTIMATE "Day: Test vs Control1" trta -1 0 1 trta*parcat5 -1 0 0 0 1 0, "Day: Test vs Control2" trta 0 -1 1 trta*parcat5 0 0 -1 0 1 0, "Night: Test vs Control2" trta 0 -1 1 trta*parcat5 0 0 0 -1 0 1 / ADJUST=bonferroni CL ILINK EXP ;

RUN;

Where ads: Analysis dataset subjid: subject identification sexn: Gender driveseq: Lens wear sequence (6 levels) asper: Study Period (3 levels) trta: Study lens type (Test, Control1, Control2) parcat5: Driving time (day or night) carry1a: First order carryover effect covariance matrix: Compound Symmetry (CS) and Unstructured (UN)

Pedestrian Distance Recognition and Road Sign Recognition

PROC GLIMMIX DATA= ads;

CLASS driveseq asper trta carry1a parcat5 sexn; MODEL aval= age sexn driveseq asper|parcat5 trta|parcat5 carry1a / DDFM=KR2 S; RANDOM INTERCEPT / SUBJECT=subjid; RANDOM INTERCEPT / SUBJECT = parcat5(subjid); *only included if ANTE(1)is used; RANDOM asper / RESIDUAL SUBJECT=time (subjid) TYPE=covariance_matrix; LSMEANS trta*parcat5 /slicediff = parcat5 CL ; **Secondary analysis; ESTIMATE "Night: Test vs Control1" trta -1 01 trta*parcat5 0 -1 0 0 0 1 / CL ; **Other Analysis; ESTIMATE "Day: Test vs Control1" trta -1 01 trta*parcat5 -1 0 0 0 1 0, "Day: Test vs Control2" trta 0 -1 1 trta*parcat5 0 0 -1 0 1 0, "Night: Test vs Control2" trta 0 -1 1 trta*parcat5 0 0 0 -1 0 1 / ADJUST= bonferroni CL ;

RUN;

Where ads: Analysis dataset subjid: subject identification driveseq: Lens wear sequence (6 levels) asper: Study Period (3 levels) trta: Study lens type (Test, Control1, Control2) parcat5: Driving time (day or night) carry1a: First order carryover effect covariance_matrix: CS, CSH, UN and ANTE(1). The covariance structure that returns the lowest AICC will be selected as the structure that best fit the data.

REFERENCES

- 1. SAS Institute Inc: SAS® 9.4 Statements: Reference, Third Edition. Cary, NC: SAS Institute Inc; 2014.
- 2. SAS Institute Inc. 2015. SAS/STAT® 14.1 User's Guide. Cary, NC: SAS Institute Inc.
- 5. Wood, JM. (2002), Age and Visual Impairment Decrease Driving Performance as Measured on a Closed-Road Circuit. ProQuest Health and Medical Complete 44(3) 482
- Wood, JM., & Carberry TP. (2006), Bilateral cataract surgery and driving performance. Br. J. Ophthalmol 90, 1277-1280
- 8. Hickson L., et al. (2010), Hearing Impairment Affects Older People's Ability to Drive in the Presence of Distracters. The American Geriatrics Society 58: 1097-1103

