1.4. Statistical Hypotheses for Study Objectives

1.4.1. Primary Hypotheses

1. The Test lens will be non-inferior to the Control 1 lens with respect to overall night driving performance. A non-inferiority margin of -0.25 will be used.

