1.5. Sample Size Justification

The study is designed and powered to demonstrate non-inferiority of the Test lens relative to the Control 1 lens with respect to night driving performance score. Assuming no difference between the Test and Control 1 lens, the sample size was calculated using a non-inferiority margin of -0.25. The sample size of 24 subjects is consider sufficiently large to test for non-inferiority with a minimum power of 80% and a two-sided type I error of 0.05. The plan is to enroll 28 eligible subjects with a target completion of 24 subjects. During the enrollment period, the subject dropout rate will be closely monitored, if an unexpectedly high dropout rate is observed, the target enrollment will be increased accordingly to ensure a minimum of 24 subjects per group complete the study.

The non-inferiority margin and sample size calculations were based on available historical data from 6 published papers between 2009 and 2015 and from an investigator initiated study (IIS) sponsored by JJVC in 2016 that examined the effect of vision condition on driving performance. The Table below summarizes the studies considered in the meta-analysis.

I able 1: Summary of published papers considered in the meta-analysis Sample Age Driving Study Vision							
Year	Author	Paper Title	Sample Size	Age (Mean)	Driving Time	Study Group	Vision Condition
						Young	Corrected
						Middle-Age	Corrected
		Age and Visual				Older	Uncorrected
2002	Wood, JM	Impairment Decrease Driving Performance as	139	57.4	Day & Night	Older with ocular disease	Uncorrected
		Measured on a Closed-Circuit Road				older with moderate / severe ocular disease	Uncorrected
		Effects of Age				Young	Corrected
2005	Chaparro, A. et al.	Auditory and Visual Dual Tasks on Closed-Road Driving Performance	28	48.3	Day	Older	Uncorrected
2006	Wood,	Bilateral cataract	47	71.1	D	Normal vision	Corrected
2006	JM. et al.	surgery and driving performance	47	71.1	Day	Cataract	Uncorrected
	Wood, JM. et al.	Interaction between visual status, driver age and distracters on daytime driving performance	39	47.9		Normal vision	Corrected
2009					Day	Blur	Uncorrected
						Cataract	Uncorrected
	Wood, JM. et al.	Effects of Simulated Visual Impairment on Nighttime Driving Performance	20	27.5	Night	Normal vision	Corrected
2010						Refractive blur	Uncorrected
						Simulated cataract	Uncorrected
2012	Wood,	Useful Field of View Predicts Driving in	02	73.6	Day	Driving without visual distraction	Corrected

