5.2. Primary Analysis Methods

Overall driving performance score will be analyzed using a linear mixed model; sequence of lens wear, period, lens type, first order carry-over, driving time (day or night) and the 2-way interactions: lens*time, sequence*time, period*time and carry*time will be included in the model as fixed effects. Age will be included as fixed covariate when appropriate. An appropriate covariance structure will be selected to model the correlation between measurements across periods within the same subject and driving time. Covariance structures that will be considered include:

- Compound Symmetry (CS)
- Heterogeneous Compound Symmetry (CSH)
- Unstructured (UN)
- Ante-dependence (ANTE(1))

For ANTE(1) structure, subject and driving time nested within subject will be included in the model as random effects. For the remaining structures only subject will be included as random effect. The covariance structure that returns the lowest Akaike Information Criteria Corrected (AICC) will be selected as the structure that best fit the data¹². Heterogeneous residuals covariance structures (R-side) across driving time will be considered when appropriate. The log-likelihood ratio test will be used to test for the homogeneity between the residual covariance structures. The Kenward and Roger method will be used for the denominator degree of freedom. Non-significant interactions at the 15% significance level will be excluded from the model. The interaction between lens type and driving time will be forced into the final model.

Comparisons between Test and Control 1 will be conducted overall across driving time and within each level of driving time. Results from the final selected model will be reported as least-square mean (LSM) differences with 95% confidence intervals.

The null and alternative hypotheses for non-inferiority of Test lens relative to Control 1 are as follows:

$$H_0: \mu_T - \mu_C \le -0.25 H_A: \mu_T - \mu_C > -0.25,$$

where μ_T and μ_C are the means of night driving performance score for Test and Control 1, respectively. Non-inferiority of the Test relative to Control 1 will be concluded if the lower limit of the 95% confidence interval of the LSM difference between Test and Control 1, at night driving time, is greater than - 0.25.

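### The primary-model code pools day and night residual variances exactly when the test says they differ, so the night non-inferiority interval can have the wrong width

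*SAP*

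**What the plan says.** In the primary-endpoint code of SAP Appendix A, the residual statement carries "group=parcat5", so day and night each have their own residual covariance parameters. A `COVTEST` homogeneity statement follows, annotated "test for homogeneity used along with GROUP = time". The rule for acting on the result is a code comment: "Remove GROUP = time from the statement above if the test for homogeneity is rejected at 5% significance level".

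SAP 5.2 says "Heterogeneous residuals covariance structures (R-side) across driving time will be considered when appropriate" and "The log-likelihood ratio test will be used to test for the homogeneity between the residual covariance structures". Protocol 14.5 has the same two sentences. Neither place says which test result leads to which model. SAP 1.1 makes the SAP the final guidance and lets it override section 14 of the protocol.

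The primary decision uses this model. Non-inferiority is "concluded if the lower limit of the 95% confidence interval of the LSM difference between Test and Control 1", at night, lies above the margin. On the margin, SAP 1.4.1 states: "A non-inferiority margin of -0.25 will be used".

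**The concern.** The null hypothesis of the homogeneity test is that day and night share the same residual covariance. Rejection is a reason to keep the grouping, and only non-rejection could justify removing it. The comment says the opposite.

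The primary contrast is a night-only difference, so its standard error should reflect night variability. A wrongly pooled variance brings day variability into the night interval. If night is the more variable condition, the interval is too narrow and false claims of non-inferiority become more frequent. If day is the more variable, the interval is too wide and power is lost.

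Unequal variances are plausible. Daytime runs require more than 1000 lux and night runs less than 10 lux (protocol 7.2, step 3.10), and the SAP itself plans for heterogeneity. The Z-scores are taken relative to the whole group across conditions (SAP 5.1). If that means one standardisation over day and night together, it would not equalise their spread.

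**Working it through.** **1. Direction of the rule**

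| Homogeneity test at 5% | What it indicates | Consistent action | Appendix A |
|---|---|---|---|
| Rejected | Day and night differ | Keep GROUP | Remove GROUP |
| Not rejected | No difference shown | Pooling is defensible | Keep GROUP (by implication) |

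The appendix is reversed in both rows. Only the first row does harm, because keeping separate variances is valid even when they are equal.

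**2. Inputs**

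- From the SAP: 24 completers, six Williams sequences, three periods per driving time, margin -0.25, two-sided 95% interval (one-sided 2.5%), true difference 0 for power.
- Night residual variance: the SAP has no figure for the pooling rule, but its power table (SAP 1.5, Table 2) fixes the variance scale. Take within-subject variance = 0.05 × (1 − ICC)/ICC, a two-sample t test with 12 per group, difference 0.25 and one-sided alpha 0.05. Power is then 69.9 / 84.3 / 94.6% at ICC 0.40 / 0.50 / 0.60, against the stated 71 / 85 / 95%. At ICC 0.50 the within-subject variance is 0.05 × 0.5/0.5 = 0.05, which is used below. (That one-sided 0.05 reproduces the table, rather than 0.025, is a separate matter.)
- Assumption: the night:day variance ratio *r*. The documents give none, so it runs from 1:4 to 4:1.

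**3. Effect of pooling on the night standard error**

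Pooled variance = (σ²_night + σ²_day)/2, so the standard error is multiplied by √[(1 + 1/r)/2]:

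- 4:1: √(1.25/2) = 0.79
- 3:1: √(1.333/2) = 0.82
- 2:1: √(1.5/2) = 0.87
- 1:2: √(3/2) = 1.22
- 1:3: √(4/2) = 1.41
- 1:4: √(5/2) = 1.58

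Check at 2:1 if one always pooled: 1.96 × 0.866 = 1.70, and the upper normal tail beyond it is 4.5%.

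**4. Simulation of the whole rule**

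Subject, period, lens and first-order carry-over are fitted within each driving time. This uses 24 + 2 + 2 + 2 = 30 parameters, leaving 72 − 30 = 42 residual df. The Test minus Control 1 contrast has variance 0.104 × σ². Homogeneity is tested by 2ν ln s²_pooled − ν ln s²_night − ν ln s²_day (ν = 42) against chi-square on 1 df at 5%. There are 100,000 trials per setting.

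| Night:day | Homogeneity rejected | Error, as written | Error, reversed rule | Error, always separate | Power, as written | Power, reversed rule |
|---|---|---|---|---|---|---|
| 1:4 | 99.3% | 0.1% | 2.5% | 2.5% | 62.7% | 92.4% |
| 1:3 | 94.2% | 0.4% | 2.5% | 2.5% | 74.4% | 92.1% |
| 1:2 | 60.8% | 1.1% | 2.2% | 2.5% | 86.3% | 90.7% |
| 1:1 | 5.1% | 2.5% | 2.5% | 2.5% | 92.4% | 92.8% |
| 2:1 | 60.6% | 3.9% | 3.1% | 2.5% | 95.2% | 93.0% |
| 3:1 | 94.2% | 5.3% | 2.6% | 2.5% | 96.6% | 92.4% |
| 4:1 | 99.3% | 6.0% | 2.5% | 2.5% | 97.0% | 92.5% |

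Error is one-sided at the margin. The higher power as written at 2:1 and above comes from the inflated error and is not a gain. A repeat with 400,000 trials gives 3.8%, 5.4% and 6.1% as written at 2:1, 3:1 and 4:1.

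Power near 92% should not be set against the SAP's 85%. The crossover contrast has variance 0.104 × 0.05 = 0.0052, while the two-sample form has (2/12) × 0.05 = 0.0083, and the alpha differs.

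**The case against.** The inversion itself cannot be argued away, but its importance can be contested.

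- **The harm is conditional.** It needs unequal variances and a rejected test. At intermediate ratios (same set-up, 40,000 trials each) the rule as written gives 2.8% at 1.25:1 and 3.1% at 1.5:1, against 3.1% and 3.3% for the reversed rule. Up to about 1.5:1 it is therefore no worse than simply reversing the comment. Nothing in the documents shows a ratio of 2:1 or more, or which condition is the more variable. This stands and limits the size of the claim.
- **The simulated model is simpler than the SAP's.** The SAP selects among four covariance structures by AICC, so the homogeneity test covers at least two parameters per driving time. A rough two-parameter compound-symmetry version gives 3.8% as written and 3.4% reversed at 2:1. This stands too: it moves the figures modestly and leaves the direction unchanged.
- **The intent may be clear.** SAP 5.2, read naturally, means heterogeneous structures when homogeneity fails, and the error is only a comment in sample code that also names a variable, `time`, which that code does not use. A careful programmer might do the right thing. But 5.2 never states the direction, and the second statistician checks compliance with the SAP (SAP 11.2), so that review could endorse the literal instruction. Departing from it becomes a change to the primary analysis that must be documented and justified (SAP 11.3). This point does not remove the need for correction.

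**Conclusion.** The concern holds. The only explicit rule for choosing between pooled and separate day and night residual covariance in the primary model is the wrong way round, and no other text corrects it. When the variances differ and the test rejects, the night interval that decides the primary hypothesis has the wrong width.

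At assumed night:day ratios of 3:1 to 4:1, one-sided error is 5.3% to 6.0%, slightly more than twice the nominal 2.5%. At 1:3 to 1:4, power falls by 92.1 − 74.4 = 17.7 to 92.4 − 62.7 = 29.7 percentage points. With equal variances the effect is negligible.

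These sizes rest on assumed ratios, a night residual variance of 0.05 and one residual variance per driving time. The finding that the rule is inverted rests on none of them. Because it governs the sole primary hypothesis, it should be corrected before the model is run on unmasked data.

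**What to change.** Preferred: keep `GROUP=parcat5` in the primary model unconditionally, delete the instruction to remove it, and say so in SAP 5.2. In the simulation this holds the error at about 2.5% at every ratio. If the variances are in fact equal, the price is small: an interval half-width of 0.146 rather than 0.144.

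Second choice, if the pre-test is retained: state in both Appendix A and SAP 5.2 that `GROUP=parcat5` is removed only when homogeneity is not rejected at 5%, and is kept otherwise. This corrects the direction but leaves about 3% error at ratios of 1.25:1 to 2:1.

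In the same edit, replace `time` in the comments with `parcat5`. Also bring the code for pedestrian and sign recognition distance into line with SAP 6.2, which describes the same homogeneity test although that code has neither a GROUP option nor a `COVTEST` statement.

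The correction to the primary model is one line of code comment and one sentence in SAP 5.2. It has no effect on data collection or enrolment.

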Proportion of correctly identified sings and proportion of hazard avoidance will be analyzed separately using a generalized linear mixed model with beta distribution and logit link function. Each model will include sequence, period, lens type, first order carry-over, driving time (day or night), and the 2-way interactions: lens*time, sequence*time, period*time and carry*time as fixed effect factors. An unstructured covariance matrix (UN) will be used to model the correlation between measurements from the same subject across periods. If convergence problems are encountered with the unstructured covariance matrix, a model with compound symmetry covariance matrix (CS) will be considered. Non-significant interactions at the 15% significance level will be excluded from the model. The interaction between lens type and driving time will be forced into the final model.

The null and alternative hypotheses for no-difference between Test and Control 1 are as follows:

$$\begin{array}{l} H_0: OR = 1 \\ H_A: OR \neq 1, \end{array}$$

where OR is the odds ratio of hazard avoidance at night driving time of Test over Control 1. No statistical difference between Test and Control 1 will be concluded if 1 falls within the 95% confidence interval of the odds ratio.

Pedestrian Distance Recognition and Road Sign Recognition

Pedestrian distance recognition and road sign recognition distance (or log-transformed distance) will be analyzed separately using a linear mixed model; sequence of lens wear, period, lens type, first order carry-over, driving time (day or night), and the 2-way interactions: lens*time, sequence*time, period*time and carry*time will be included in the model as fixed effects. Age will be included as fixed covariate when appropriate. An appropriate covariance structure will be

selected to model the correlation between measurements across periods within the same subject and driving time. Covariance structures that will be considered include:

- Compound Symmetry (CS)
- Heterogeneous Compound Symmetry (CSH)
- Unstructured (UN)
- Ante-dependence (ANTE(1))

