For ANTE(1) structure, subject and driving time nested within subject will be included in the model as random effects. For the remaining structures only subject will be included as random effect. The covariance structure that returns the lowest Akaike Information Criteria Corrected (AICC) will be selected as the structure that best fit the data¹². Heterogeneous residuals covariance structures (R-side) across driving time will be considered when appropriate. The log-likelihood ratio test will be used to test for the homogeneity between the residual covariance structures. The Kenward and Roger method will be used for the denominator degree of freedom. Non-significant interactions at the 15% significance level will be excluded from the model. The interaction between lens type and driving time will be forced into the final model.

Results from the final selected model will be reported as least-square mean (LSM) estimates with 95% confidence intervals.

The null and alternative hypotheses for non-inferiority of Test lens relative to Control 1 are as follows:

$$H_0: \mu_T - \mu_C = 0$$

$$H_A: \mu_T - \mu_C \neq 0,$$

where $\mu_T - \mu_C$ is the mean difference of distance recognition at night driving between Test and Control 1. No statistical difference between Test and Control 1 will be concluded if 0 falls within the 95% confidence interval of the LSM difference between Test and Control 1.

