7. OTHER ANALYSIS

Further comparisons between the test lens and the control lenses will be conducted using the same models described in the primary and secondary analysis sections 5.2 and 6.2. The following hypotheses will be tested:

- The Test lens will be non-inferior to at least one of the Control lenses (Control 1 or Control 2) lens with respect to overall daytime driving performance. A non-inferiority margin of -0.25 will be used.
- 2. The Test lens will be non-inferior to the Control 2 lens with respect to overall night driving performance. A non-inferiority margin of -0.25 will be used.

- 3. The Test lens will be non-inferior to the Control 2 lens with respect to binocular low luminance high contrast visual acuity. A non-inferiority margin of 0.1 LogMAR will be used.
- 4. The Test lens will be no different than the Control 2 lens with respect to low luminance low contrast threshold without glare.
- 5. The Test lens will be no different than the Control 2 lens with respect to the percentage of road signs correctly identified at night driving.
- 6. The Test lens will be no different than the Control 2 lens with respect to average distance to correctly identify a pre-determined road sign at night driving.
- 7. The Test lens will be no different than the Control 2 lens with respect to the percentage of hazards avoided at night driving.
- 8. The Test lens will be no different than the Control 2 with respect to average pedestrian recognition distance at night driving.

Multiple comparisons between the test lens and the control lenses with respect to driving performance (Hypotheses 1 and 2) will be adjusted to control for type I error using bonferroni's method. For the remaining hypotheses, the comparisons will be conducted with a two-sided type I error rate of 5%.

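### The Appendix A code for the secondary driving endpoints does not carry out the models in SAP 6.2 and 7 and, depending on the data, can give wrong night intervals

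*SAP*

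**What the plan says.** **Interactions.** For the two recognition distances, SAP 6.2 says the "2-way interactions: lens*time, sequence*time, period*time and carry*time will be included in the model as fixed effects". For sign and hazard percentages it lists the same terms: "2-way interactions: lens*time, sequence*time, period*time and carry*time as fixed effect factors". Interactions not significant at 15% are then dropped, except lens by time, which is forced in. The Appendix A statement for sign and hazard percentages is "MODEL aval= age sexn driveseq asper|parcat5 trta|parcat5 carry1a / DDFM=KR2 S DIST=BETA LINK=LOGIT"; for the distances it is "MODEL aval= age sexn driveseq asper|parcat5 trta|parcat5 carry1a / DDFM=KR2 S". In both, sequence and carry-over enter as main effects only.

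**Residual covariance, distances.** SAP 6.2 says "Heterogeneous residuals covariance structures (R-side) across driving time will be considered when appropriate" and adds, without condition, that a likelihood ratio test of homogeneity will be used. The code line is "RANDOM asper / RESIDUAL SUBJECT=time (subjid) TYPE=covariance_matrix". It has no `GROUP=`, and no `COVTEST` follows. Driving time is defined for this block as `parcat5`; `time` is not defined, and `subjid` is not in the `CLASS` list.

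**Multiplicity.** SAP 7 applies Bonferroni to its hypotheses 1 and 2, both on overall driving performance. Of the rest it says: "For the remaining hypotheses, the comparisons will be conducted with a two-sided type I error rate of 5" percent. In both secondary driving blocks the second `ESTIMATE` statement, covering three contrasts, carries `ADJUST=bonferroni`.

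**Comparators.** The primary block of Appendix A has all four interactions, `GROUP=` and `COVTEST`. Protocol 14.6 has only lens by time and period by time, as the secondary code does, but SAP 1.1 says the SAP supersedes Protocol section 14.

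**The concern.** Text and code describe different analyses of the same endpoints, and the code matches the interaction list that the SAP replaced. A term that never enters the model cannot be tested at 15%, so the rule for dropping terms cannot be followed. Without `GROUP=` and `COVTEST`, the homogeneity test cannot be run and day and night share one residual covariance.

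Interval width matters here because each secondary driving claim is one of no difference, concluded when the night 95% interval for Test versus Control 1 contains 0 (distances) or 1 (odds ratios). An interval that is too wide makes the claim easier; one that is too narrow makes it harder and under-covers.

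**Working it through.** **1. Side by side**

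| Item | SAP text | Sign/hazard code | Distance code | Primary code |
|---|---|---|---|---|
| Lens by time | yes | yes | yes | yes |
| Period by time | yes | yes | yes | yes |
| Sequence by time | yes | no | no | yes |
| Carry-over by time | yes | no | no | yes |
| Day/night homogeneity test | distances and primary | not promised | absent | present |
| Bonferroni | SAP 7 hypotheses 1 and 2 only | applied | applied | applied |

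**2. Inputs for the size.** From the SAP: 24 completers (1.5), and six Williams sequences in three periods within each driving time (1.6), so 24/6 = 4 subjects per sequence. Assumptions: complete data, a random subject effect, independent residuals within driving time (a compound-symmetry-type case), and normal quantiles. The documents give no day or night SD, so the ratio r = day SD / night SD is varied. The plan states no figure to reproduce here. The results were obtained by generalised least squares on the design matrix; the closed forms below give the same values. They apply to the linear distance models, not directly to the beta models.

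**3. Omitted interactions: precision.** Take the night Test minus Control 1 contrast with within-subject SD 1. Its variance without any carry-over term is 2/24 = 1/12.
- SAP text: carry-over is estimated from night data alone, which adds 1/48. SE = sqrt(1/12 + 1/48) = sqrt(0.10417) = 0.323.
- Code: one carry-over term is estimated from day and night together, which adds half as much. SE = sqrt(1/12 + 1/96) = sqrt(0.09375) = 0.306.
- Ratio = sqrt(0.09375/0.10417) = 0.949, so the code's interval is about 5% narrower.

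**4. Omitted interactions: bias.** Control 1 directly follows Test in two of the six sequences (sequences 1 and 5), and Test never follows itself. A carry-over of 1 from Test therefore shifts the unadjusted Test minus Control 1 contrast by -2/6 = -1/3. If it occurs only at night, a common carry-over term estimates half of it and removes half the shift, leaving -1/6. The model in the text leaves zero. Night-only carry-over from Control 1 gives +1/6.

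**5. Pooled residual variance, under the code's terms.** Night variance is 1, day variance r², and the pooled value (1 + r²)/2.
- Variance the code reports: 0.09375 × (1 + r²)/2.
- True variance of the same estimate: 1/12 + (1/48) × (1 + r²)/4.
- Width ratio k = sqrt(reported/true); coverage = 2Φ(1.96k) - 1.

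At r = 2: reported 0.2344, true 0.1094, k = sqrt(2.143) = 1.46. At r = 0.5: reported 0.0586, true 0.0898, k = sqrt(0.652) = 0.81.

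| Day SD / night SD (assumed) | Night interval width, used/right | Coverage of nominal 95% |
|---|---|---|
| 0.5 | 0.81 | 88.7% |
| 0.8 | 0.91 | 92.7% |
| 1.0 | 1.00 | 95.0% |
| 1.25 | 1.11 | 97.1% |
| 1.5 | 1.23 | 98.4% |
| 2.0 | 1.46 | 99.6% |

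**6. Bonferroni.** Three contrasts share the adjusted statement: day versus Control 1, day versus Control 2 and night versus Control 2. The two-sided quantile at 0.05/3 is 2.394, against 1.960 at 0.05. Since 2.394/1.960 = 1.22, the adjusted intervals are about 22% wider. The night Test versus Control 1 contrast has its own unadjusted `ESTIMATE` statement in both blocks.

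**The case against.** A reader might infer that the night intervals will be wrong. The documents do not support that. Pooling is correct when day and night variances are equal; no SDs are given; SAP 6.2 makes heterogeneous structures conditional and allows log-transformed distances, which could reduce a spread that grows with the mean. Any error can go either way.

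A reader might also size the pooling effect as sqrt((1 + r²)/2), which is 1.58 at r = 2. That fits the full text model, where the night contrast uses night data alone. The printed code shares the carry-over term across day and night, and the figure is 1.46.

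Nor does the Bonferroni line reach the secondary decisions. It affects the SAP 7 night comparisons with Control 2, and day contrasts for which SAP 7 states no hypothesis on these endpoints.

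Other points for the plan have weight. The two interactions may leave the model under the 15% rule, and the code would then match an allowed reduced model. Night-only carry-over has no specific support: Protocol 7.2 uses fresh lenses for each trial and Protocol 4.2 builds in at least 20 minutes between drives. Appendix A is template syntax with a placeholder covariance type, and SAP 11.1 and 11.2 require an independent program reviewer and a second statistician.

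What remains is that the code cannot serve as the starting model or run the promised test. As printed, the distance block would probably not run at all, because `time` is undefined and `subjid` is not a class variable. That means no interval rather than a wrong one, but somebody must rewrite it, and the rewrite should follow the SAP text.

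**Conclusion.** Wrong as written, for the secondary driving endpoints and their SAP 7 counterparts only; the primary block has the four interactions, `GROUP=` and `COVTEST`. The omissions are matters of record. Their numerical effect is conditional.

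If `time` is read as `parcat5`, the distance code can give night intervals from 0.81 to 1.46 times the right width for day/night SD ratios of 0.5 to 2, with no effect at 1. Dropping the two interactions narrows the interval by about 5% and biases the contrast by one sixth of any night-only carry-over from Test. With equal variances and no carry-over that differs by time, the code's interval is valid. The size figures rest on the assumed SD ratio, complete data from 24 subjects and a compound-symmetry-type model. The Bonferroni line makes a finding of no difference from Control 2 easier wherever the adjusted intervals are the ones reported.

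**What to change.** Before unmasking, bring Appendix A into line with SAP 6.2 and 7:

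- In both blocks, replace `driveseq` and `carry1a` with `driveseq|parcat5` and `carry1a|parcat5`, subject to the 15% rule.
- In the distance block, use `SUBJECT=parcat5(subjid)` with `GROUP=parcat5`, and add the `COVTEST` homogeneity statement. Keep `GROUP=` when homogeneity is rejected and drop it otherwise. The comment in the primary block states this the wrong way round, so it should be corrected there and not copied.
- Add `subjid` to the `CLASS` statement in both blocks.
- Remove `ADJUST=bonferroni` from both blocks.

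The cost is a few lines of code, and a slightly larger SE (0.323 instead of 0.306 within-subject SD) if the extra terms stay in.
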